# SPECIFIC AIMS

**Primary:** To compare IN-OXT vs. placebo on changes on the Hyperphagia Questionnaire-Clinical Trials (HQ-CT) from baseline to week 8 in children with PWS. We hypothesize that IN-OXT will be significantly superior to placebo in improving hyperphagia.

Secondary: To compare the change from baseline to week-8 of IN-OXT vs. placebo on:

- 1. Repetitive Behavior Scale-Revised (RBS-R).
  - We hypothesize that IN-OXT will significantly reduce repetitive behaviors from baseline to endpoint as measured by a reduction of the score on the RBS-R when compared to placebo.
  - We hypothesize that IN-OXT will significantly reduce rigid behaviors from baseline to endpoint as measured by a reduction of the score on the MERS-PWS when compared to placebo.
- 2. Weight, BMI (z-score) and Body composition via bioelectrical impedance analysis
  - We hypothesize that IN-OXT will significantly reduce weight and BMI compared to placebo.
  - We hypothesize that IN-OXT will significantly reduce body fat compared to placebo, as measured by body composition via bioelectrical impedance analysis.
- 3. Quality of Life Measures
  - We hypothesize that IN-OXT will improve quality of life measured by an increase in overall score on the WHOQOL from baseline to endpoint when compared to placebo.
  - We hypothesize that IN-OXT will improve quality of life measured by a reduction in overall score on the CSQ from baseline to endpoint when compared to placebo.
- 4. Salivary Oxytocin Concentration
  - We hypothesize that higher concentrations of salivary oxytocin will be correlated with positive changes on each outcome measure, indicating improvement in symptoms.
- 5. Safety Analyses
  - We hypothesize that IN-OXT will not increase side-effect burden from baseline to endpoint compared to placebo.

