#### Titration Schedule:

Adverse events: Study physician will review with study participants regarding the nature,

duration and severity of noted adverse events. The study physician will make clinical judgements on the relationship between reported adverse events with study medication. If there is a high likelihood of adverse events being related drug effects, the subject will titrate down from 16 IU/day (4 sprays per day) to 12 IU/day (3 sprays per day) and will be reassessed in one week). At the next assessment the side effects and tolerability will again be reviewed by the PI and medical monitor. If the side effects have resolved, the subject will be titrated back up to 16 IU/day. If the side effects persist, the subject may continue on the 12 IU/day for another week; or will be discontinued from the study at the judgement of the PI. Subjects who do not receive the full dose by week four will be discontinued. Any subject who is discontinued from the study will be referred for continued medical follow up.

Lack of response: One upward titration will be allowed at week 2 to 24 IU/day (4 sprays per day) if study clinician, with consultation of the PI, determines that study subject experiences no response on hyperphagia via a categorical yes/no determination, and has no adverse events. In our current ongoing pilot study, and in [name]'s study, the initial hyperphagia response was observed at the week 1 and week 2 ratings.

**Instructions for Dosing:** Once the cap has been removed from the spray, the device should be held upright to the nostril and the actuator depressed. The patient should be in the sitting position and should be instructed to inhale gently through the nose while the actuator is being depressed. The head should be tilted back once the actuator is depressed to ensure that no fluid runs out of the nose. Parents may assist the child with dosing.

**Outcome Measures:** Project outcomes will be determined by changes in scores of parent and clinician rated measures from baseline to week 8 and comparisons of week 8 measures between active treatment and placebo groups. Assessments will be administered according to the schedule of events in **Table 2**.

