#### Independent Data Safety Monitoring Committee

An Independent Data Safety Monitoring Committee (DSMC) will review safety and clinical outcome data including data on adverse events (AEs) and serious adverse events (SAEs) at regular intervals. They will meet biannually to review study reports. The DSMC will be independent of the investigator and will be empowered to recommend stopping the study due to safety concerns, but not for efficacy or futility. The DSMC may review blinded, unblinded, or partially unblinded data, but the investigator will remain blinded until the official unblinding of the database.

**Statistical Analyses:** Analyses will be based on the intent-to-treat approach in which subjects are analyzed in the group to which they were originally assigned regardless of treatment compliance. All variables will be initially screened for inconsistent or abnormal values, and continuous measures will be assessed for skew and outliers. Transformations to improve normality will be applied when necessary. The demographic characteristics of all randomized patients will first be summarized using standard descriptive statistics (means, medians, standard deviations, and ranges for continuous variables and frequencies for categorical variables). Although subjects will be randomized 1:1 to the two treatment groups, imbalances in patient characteristics may still occur by chance given the limited sample size of the Phase 2 trial. Between group differences in the baseline demographic and other prognostic variables will be assessed using the chi- square test for discrete variables and the T-test or Wilcoxon rank sum test for continuous variables. Baseline characteristics which are found to be significantly different will be considered for inclusions as potential confounders in secondary analyses of treatment effects.

Summary of Analytic Approach: The primary outcome measure is change on the continuous measure of the Hyperphagia Questionnaire-Clinical Trials, a valid and reliable measure of the food seeking pathology in PWS. Secondary outcome measures include a measure of repetitive behavior (RBS-R and MERS-PWS), weight, measures of Quality of Life and Global Functioning (WHOQOL, CGI), and measures of salivary Oxytocin concentration. Given that these outcomes are all continuous variables, they will be analyzed using the same general statistical strategy as outlined below.

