#### **Detailed Description of Analyses**

**Primary Analyses**: Analyses for Specific Aim (1): To compare IN-OXT vs. placebo with respect to improvement in the hyperphagia severity in children with PWS via improvement in scores on the Hyperphagia Questionnaire-Clinical Trials.

The primary analysis will evaluate the hypothesis that IN-OXT will decrease hyperphagia vs. placebo.

- 1. Response to treatment will be assessed in two ways:
  - a. The effects of IN-OXT on hyperphagia will be analyzed using an intent-totreat approach with the two-sample T-test or Wilcoxon rank sum tests to compare treatment groups at specific visits as well as linear mixed effects models to analyze the repeated measures and changes over time.
  - b. The proportion of responders in each treatment group will also be compared. Response will be defined as a 30% or greater decrease in food-seeking and eating behaviors from baseline on the Hyperphagia Questionnaire-Clinical Trials. Dropouts for clinical reasons will be coded as non- responders. Differences in the proportion of responders in each treatment group will be evaluated using the chi-square test and time to response will be assessed using survival analytic techniques.
  - c. All tests will be two-tailed with an alpha level of 0.05.

**Secondary Analyses:** Analyses for Specific Aims (2) through (8): To compare IN-OXT vs. placebo in children with PWS on change in:(2) Repetitive behaviors via scores on the Repetitive Behavior Scale – Revised (RBS-R) and Montefiore-Einstein Rigidity Scale-Revised (MERS-PWS)(3) Weight and body composition via impedance analysis. (4) Quality of Life Measures on the World Health Organization Quality of Life Scale (WHOQOL)(5) Clinical Global Impression Scale (CGI-I) (6) Salivary Oxytocin Concentration (7) Safety Analyses

IN-OXT and placebo groups will be compared to the above secondary measures will be analyzed using methods similar to those outlined above. Associations between outcome measures at a specific time point will be analyzed with the Spearman rank or Pearson correlation coefficient.

- 1. Secondary Aim (1) Repetitive Behaviors
  - *a.* The effects of treatment on frequency and severity of repetitive behaviors will be assessed by fitting linear mixed effects models to the data on the RBS-R scores. We hypothesize that IN- OXT will significantly reduce repetitive behaviors from baseline to endpoint compared to Placebo.

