**Power Analysis: Sample size justification:** The target sample size for this Phase 2 trial is 25 patients per treatment group. The power for the study has been calculated to generate a detectable signal with the sample size of 50 subjects. With this sample size, the study will have 80% power to detect a minimum effect size of d= 0.8 standard deviations in the outcome measures between groups using a two-sample T-test and a two sided Type I error rate of 5%. The study is powered based on a conservative estimate from a heterogeneous population. We expect that in this homogeneous PWS population selected to match study drug to underlying mechanism, the true power will exceed the conservative estimate. This minimum detectable difference is smaller than the treatment effects observed in our previous studies of IN-OXT in adults with ASD, which demonstrated an effect size of d=1.2 on a social cognition measure (RMET) [3], and an effect size of d = 0.84 on a quality of life measure (WHOQOL) [3]. In addition, our previous study of a V1a antagonist in adults with ASD demonstrated an effect size of d=0.8 on a social cognition measure (ASR Lust) [80], and an effect size of d = 0.8 on an Eye Tracking measure (Biological Motion Preference) [90]. The above effect sizes observed in our pilot data were based on a heterogeneous sample of ASD patients characterized by over 100 known different genetic contributing factors. In the proposed trial, both males and females will be included, and any heterogeneity in outcomes due to gender may attenuate overall treatment differences. However, by selecting an orphan population (PWS) with a single unique genetic contribution, and selecting a treatment that matches the known molecular mechanism (IN-OXT), we expect that the treatment effects in this study will nevertheless be greater than the effects observed in earlier studies.

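### The primary analysis section lists several HQ-CT tests for Aim 1, each at two-sided 0.05, and names none of them as the deciding test

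*Combined protocol and SAP*

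**What the plan says.** **Aim and endpoint.** The Specific Aims set Aim 1 as IN-OXT against placebo on HQ-CT change from baseline to week 8, with the hypothesis "We hypothesize that IN-OXT will be significantly superior to placebo in improving hyperphagia". The Summary of Analytic Approach agrees: "The primary outcome measure is change on the continuous measure of the Hyperphagia Questionnaire-Clinical Trials".

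**Primary Analyses (under Detailed Description of Analyses).** One hypothesis is stated, then "Response to treatment will be assessed in two ways":
- Branch (a): "two-sample T-test or Wilcoxon rank sum tests to compare treatment groups at specific visits as well as linear mixed effects models". The visits are not named.
- Branch (b): a chi-square test on the proportion with at least a 30% fall in HQ-CT; in addition, "time to response will be assessed using survival analytic techniques".
- Item (c): "All tests will be two-tailed with an alpha level of 0.05".

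**Other places that bear on the choice.**
- Outcome Measures, after the Titration Schedule, bases outcomes on "changes in scores of parent and clinician rated measures from baseline to week 8 and comparisons of week 8 measures between" the two groups, so both change and level are in play.
- The Summary of Analytic Approach compares week-8 levels and also change. For change, it uses a two-sample test if an exploratory look shows no dependence on baseline, and ANCOVA otherwise. No criterion for dependence is given. It also declines multiplicity adjustment, on the ground that several different outcomes are analysed in an exploratory study.
- The Missing data paragraph says that the primary analysis uses the data available at each time point, and then argues for the mixed model.
- The Power Analysis claims 80% power at d = 0.8 with 25 per group, "using a two-sample T-test and a two sided Type I error rate of 5" per cent. It does not say on which HQ-CT quantity or at which visit.

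**The concern.** The plan does not say which result answers Aim 1. At least four analyses stand under the one primary hypothesis with equal alpha and no order: a two-sample test, a mixed model, a responder test and a time-to-response analysis. HQ-CT is collected at weeks 2, 4, 6, 8 and 10, so the unnamed visits multiply the two-sample tests further. If these analyses disagree, the choice of headline is made after the results are known.

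The sentence that declines multiplicity adjustment does not settle this. It speaks of different outcomes, whereas the issue here is several analyses of one outcome. An exploratory Phase 2 trial may reasonably leave out adjustment. But the trial is meant to generate data for Phase 3, it states a superiority hypothesis, and it claims 80% power. Its primary result should therefore be identifiable in advance.

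**Working it through.** **1. The plan's own power figure.** Inputs from the Power Analysis: 25 per group, d = 0.8, two-sided 0.05, two-sample t-test. The noncentrality is d × √(n/2) = 0.8 × √12.5 = 2.83.
- Normal approximation: Φ(2.83 − 1.96) = 80.7%.
- Noncentral t, 48 degrees of freedom: 79.1%.

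The stated 80% is reproduced.

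**2. Does any section name the decider?**

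| Section | What it fixes | What it leaves open |
|---|---|---|
| Specific Aims | HQ-CT change to week 8 | Test or model |
| Summary of Analytic Approach | Continuous change as primary outcome | Level or change; change test or ANCOVA |
| Primary Analyses | List of tests, alpha 0.05 | Visit, t-test or Wilcoxon, which branch decides |
| Missing data | Use of available data | Which model is primary |
| Power Analysis | Two-sample t-test for sizing | Quantity and visit |

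None does.

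**3. False-positive chance if any one of four tests could carry Aim 1.** The plan does not state this rule; the calculation is conditional on it.

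Upper reference, four independent tests: 1 − 0.95⁴ = 18.5%. The real tests share data, so the figure is lower and was simulated with 25 per arm and no treatment effect. The four tests were:
- t-test on week-8 change;
- t-test on per-subject slope, standing in for the time × treatment term of the mixed model;
- chi-square on at least a 30% fall at week 8;
- log-rank on first 30% fall. The plan names no specific survival test, so the log-rank is an assumption.

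Other assumptions not in the documents: scores at weeks 0, 2, 4, 6 and 8 limited to 0-36, baseline mean 16 or 20, SD 4, 6 or 8, between-visit correlation 0.5 or 0.7, a common fall of 2 or 4 points, no dropout. That makes 24 scenarios of 6,000 runs each.

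| Rule | Chance of p < 0.05 with no effect |
|---|---|
| Each test alone | 4.4-6.6% |
| t-test or responder test | 8.3-9.6% |
| Any of the four | 13.4-15.1% |

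A second simulation gave 12.2-14.8% for the same four tests (baseline mean 20, SD 6, fall of 0.5 SD, correlation 0.3-0.85 under two correlation structures).

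**4. Power of the proposed decider.** Let ρ be the assumed correlation of baseline with week-8 HQ-CT, with equal SDs σ. The SD of change is σ√(2(1 − ρ)), and the ANCOVA residual SD is σ√(1 − ρ²). An effect of 0.8 SD of change therefore becomes 0.8 × √(2/(1 + ρ)) residual SDs.
- ρ = 0.5: 0.8 × 1.155 = 0.924; noncentrality 0.924 × √12.5 = 3.27; power 89%.
- ρ = 0.7: 0.8 × 1.085 = 0.868; noncentrality 0.868 × √12.5 = 3.07; power 85%.
- t-test on change, either ρ: 79%.

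**5. The choice between change test and ANCOVA after looking at the data.** With an assumed screen for baseline dependence at p < 0.05 or p < 0.01, simulated type I error was 4.3-5.7%. Power was within about 1-3 points of always using ANCOVA.

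**The case against.** Most of the answer can be pieced together. The aim fixes change to week 8, the primary outcome is continuous change, and the sizing uses a two-sample t-test. The responder comparison is introduced as an addition. The Missing data sentence about each time point may describe only how available data are used, and the level-and-change strategy is written for all outcomes. On this view only a label is missing, in a self-described exploratory Phase 2 trial. That stands as far as the endpoint goes: a reader who inferred that the primary endpoint is undefined would be wrong. It does not supply the deciding analysis, because the section headed Primary Analyses gives the mixed model and the responder branch the same standing, and the plan's own rule may replace the change test with ANCOVA.

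Three stronger readings are tempting and are not supported.
- **That the trial runs at 13-15% type I error.** This needs an any-positive rule that the plan does not contain.
- **That choosing between change test and ANCOVA after looking inflates error.** Step 5 shows no material inflation. The reason to drop the choice is that it leaves the primary model open, with no criterion.
- **That declining multiplicity adjustment across outcomes is itself an error.** For an exploratory trial it is acceptable.

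The power contrast also depends on how d is defined. If d = 0.8 refers to the SD of the score and ρ = 0.7, the formula gives 94.7% for the change t-test and 97.2% for ANCOVA, a much smaller gap. The Power Analysis does not say which SD it means.

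**Conclusion.** The point holds in a limited form. The endpoint and time point are fixed, but the analysis that decides Aim 1 is not, and no other section settles it. That conclusion rests on the text alone.

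The size is conditional. If any of the four analyses could carry Aim 1, the false-positive chance is roughly 13-15% instead of 5%, under assumed HQ-CT mean, SD and correlation and with no dropout. The power advantage of a baseline-adjusted analysis (85-89% against 79%) assumes d = 0.8 on change, correlation 0.7-0.5, complete data and no floor effect on the score. The plan's 80% is correct for the two-sample t-test it names. This should be fixed before unblinding; it does not call the design or the sample size into question.

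**What to change.** Before unblinding, add a few sentences to Primary Analyses:

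1. **Name one deciding analysis:** the IN-OXT minus placebo difference in HQ-CT at week 8 from ANCOVA with baseline HQ-CT as covariate, two-sided 0.05. Name only this model. A mixed-model contrast can give a different answer when visits are missing, so offering both would reopen the choice.
2. **Always adjust for baseline HQ-CT.** For the primary outcome, remove the step that chooses between change test and ANCOVA after looking at the data.
3. **Keep covariates added for observed imbalance out of this model.** The opening Statistical Analyses paragraph already places them in secondary analyses, while the Summary of Analytic Approach adds them to the model. Align the second with the first.
4. **Label the rest as supportive,** reported with estimates and confidence intervals: other visits, unadjusted level and change tests, Wilcoxon or transformed analyses, the mixed model, the responder proportion and time to response.

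Sample size, visits, conduct and the power statement need no change. The cost is that a positive supportive test can no longer be presented as success on Aim 1.

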#### Additional Analyses

 Sample size permitting, we will explore the potential for ethnicity-by-treatment interactions. If effects of minority status are found that might be clinically meaningful, even if not statistically significant, we will report these to guide future research. Please see the Planned Enrollment Table for the breakdown of anticipated percentages of children of each ethnicity that will be enrolled.

- 2. We will test for gender by treatment interactions.
- 3. We will explore IQ by treatment interactions.
- 4. We will explore for co-morbidity (e.g. Type 2 Diabetes, Hypogonadism etc.) by treatment interactions.
- 5. We will explore for weight based dosing by treatment interactions.

**Missing data:** In any clinical trial, some subjects will be lost to follow up or will miss study visits but the expected rate is low given that this is only an 8 week trial. Primary analysis will be based on available data at each time point. The advantage of the linear mixed effects approach is that it can handle data which are missing at random and measurement times which are not evenly spaced. However, when the missingness mechanism depends on unobserved information, i.e., non-ignorable, parameter estimates and resulting tests on hypotheses will be biased without further adjustment. Different approaches for handling missing data will be performed in this study. Multiple imputation will be applied if missing data rates are observed to differ across observed covariates. Regardless of the technique, characteristics of patients who are lost to follow-up will be compared to those that remain in the study to assess the degree of any selection bias, and sensitivity analyses will be performed to evaluate robustness of conclusions to the different missing data approaches.

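### The responder analysis ties non-response to an undefined dropout label and gives other dropouts no stated status, so the proportion can depend on how a withdrawal is classified

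*Combined protocol and SAP*

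**What the plan says.** Under Detailed Description of Analyses, Primary Analyses, response is assessed in two ways. Item 1a covers the HQ-CT score (two-sample tests and mixed models). Item 1b covers responders: "Response will be defined as a 30% or greater decrease in food-seeking and eating behaviors from baseline on the Hyperphagia Questionnaire-Clinical Trials". The test is given as "Differences in the proportion of responders in each treatment group will be evaluated using the chi-square test", and item 1c adds "All tests will be two-tailed with an alpha level of 0.05". Item 1b names no visit for the proportion and does not say whether the chi-square is continuity-corrected. On dropouts it says only "Dropouts for clinical reasons will be coded as non- responders".

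Three other statements bear on this:

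- Statistical Analyses: "Analyses will be based on the intent-to-treat approach in which subjects are analyzed in the group to which they were originally assigned", whatever their compliance.
- Missing data (under Additional Analyses): "Primary analysis will be based on available data at each time point".
- The same paragraph: "Multiple imputation will be applied if missing data rates are observed to differ across observed covariates", and "sensitivity analyses will be performed to evaluate robustness of conclusions to the different missing data approaches".

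No section defines a clinical reason, says who assigns it or when, or gives a response status to subjects who leave for any other reason.

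**The concern.** A subject who leaves before week 8 without a score is a fixed non-responder if the withdrawal is labelled clinical. If it carries another label, the plan is silent and the available-data default applies. Two subjects with identical data can therefore contribute differently.

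The label is assigned after randomisation, and the protocol leaves room for interpretation. The Titration Schedule allows discontinuation at the investigator's judgement when side effects persist. It also requires discontinuation of subjects not on full dose by week four, without saying whether that counts as a clinical reason. A family that leaves because the spray seems not to help could be recorded as lack of response or as withdrawn consent.

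If the mix of reasons differs by arm, through tolerability or perceived benefit, the comparison of proportions can be biased. With 25 subjects per arm, each one is worth four percentage points.

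**Working it through.** **The plan's own figure.** Power Analysis states 80% power for d = 0.8 with 25 per group and two-sided 5%. The noncentrality is 0.8 × √(25/2) = 2.828. The normal approximation gives Φ(2.828 − 1.960) = 80.7%, and the exact noncentral t gives 79.1%. The figure reproduces. It concerns a t-test on a continuous outcome; no power is stated for responders.

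**Inputs.** From the documents: 25 per arm, 1:1 allocation, chi-square test, two-sided alpha 0.05. The documents give no responder rate and no dropout rate (dropout is only called low), so all counts below are assumptions.

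**Mechanism.** A dropout without a response adds one to the denominator if labelled clinical and nothing if left out. Leaving subjects out always raises the proportion in their arm. Losses left out on IN-OXT widen a difference favouring IN-OXT, and losses left out on placebo narrow it.

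**Formula.** With a and b the responders and non-responders on IN-OXT, c and d those on placebo, and N the total:

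X² = N(ad − bc)² / [(a+b)(c+d)(a+c)(b+d)]

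For the corrected version, |ad − bc| is replaced by |ad − bc| − N/2.

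**Worked pair.** Three IN-OXT subjects drop out without a response.

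- Labelled clinical: 11/25 vs 5/25. X² = 50 × 150² / (25 × 25 × 16 × 34) = 1,125,000 / 340,000 = 3.31, p = 0.069. Corrected: 50 × 125² / 340,000 = 2.30, p = 0.130.
- Labelled otherwise and left out: 11/22 vs 5/25. X² = 47 × 165² / (22 × 25 × 16 × 31) = 1,279,575 / 272,800 = 4.69, p = 0.030. Corrected: 47 × 141.5² / 272,800 = 3.45, p = 0.063.

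**Range over other assumed counts**

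| Dropouts left out (IN-OXT, placebo) | All counted as non-responders | After leaving out | Uncorrected p | Corrected p |
|---|---|---|---|---|
| 3, 0 | 11/25 vs 5/25 | 11/22 vs 5/25 | 0.069 → 0.030 | 0.130 → 0.063 |
| 3, 3 | 11/25 vs 5/25 | 11/22 vs 5/22 | 0.069 → 0.060 | 0.130 → 0.117 |
| 0, 4 | 12/25 vs 5/25 | 12/25 vs 5/21 | 0.037 → 0.090 | 0.073 → 0.166 |
| 3, 1 | 12/25 vs 6/25 | 12/22 vs 6/24 | 0.077 → 0.040 | 0.141 → 0.080 |
| 2, 0 | 12/25 vs 6/25 | 12/23 vs 6/25 | 0.077 → 0.044 | 0.141 → 0.086 |
| 0, 2 | 12/25 vs 6/25 | 12/25 vs 6/23 | 0.077 → 0.117 | 0.141 → 0.205 |
| 5, 0 | 12/25 vs 6/25 | 12/20 vs 6/25 | 0.077 → 0.014 | 0.141 → 0.032 |
| 2, 0 | 12/25 vs 5/25 | 12/23 vs 5/25 | 0.037 → 0.020 | 0.073 → 0.043 |

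With one dropout per arm and 12 vs 6 responders, the uncorrected p lies between 0.059 (12/24 vs 6/25) and 0.095 (12/25 vs 6/24), whichever labels are used. A single label can still tip a result that starts very near the threshold: 13/25 vs 6/25 gives 0.041, and 13/25 vs 6/24 gives 0.053.

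**After the fix.** With all dropouts counted as non-responders, the denominators stay at 25 and 25. The 12 vs 6 example then gives 48% vs 24%, p = 0.077 (corrected 0.141), whatever reasons are recorded.

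**The case against.** Much of the case on the other side stands.

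- **Exclusion is an inference.** A reader might take item 1b to say that other dropouts leave the denominator. It does not; it is silent. The Missing data paragraph supplies the available-data default, but it also foresees several approaches, conditional multiple imputation, a comparison of those lost with those retained, and sensitivity analyses. None is tied to item 1b. Even under imputation the label would matter, because a clinical dropout stays a fixed failure while another with the same data is imputed.
- **Intent-to-treat is not contradicted.** A reader might infer that the analysis breaches the plan's own principle. The plan defines that principle by assigned group, which does not settle how a missing response is coded.
- **This is not the main outcome.** Summary of Analytic Approach names the continuous HQ-CT change as the primary outcome, and power rests on a t-test. Both are untouched. Item 1b also plans a time-to-response analysis, which can use the HQ-CT visits before dropout. Even so, item 1b is listed under Primary Analyses at 0.05, with no adjustment for multiple testing.
- **The numbers are selected.** The clearest shifts need lopsided handling and near-threshold counts, and several vanish with continuity correction. Low dropout is expected over eight weeks, though no rate is given.
- **Blinding helps.** The investigator is blinded, which limits labelling driven by knowledge of the arm. It does not stop true reasons differing by arm. Intolerance and lack of benefit could both be called clinical, in which case both would already count as failures.
- **The remedy has its own bias.** Counting every missing score as a failure is single imputation. It would include assessments missed for reasons such as those in Special Circumstances. Defining the term in advance and classifying reasons before unblinding would be a narrower repair, but it would leave the dependence on labels in place.

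**Conclusion.** The point holds for the responder proportion in item 1b, a supporting analysis listed under Primary Analyses. One class of dropout has a fixed outcome, the class is undefined, and the rest are most naturally omitted under the available-data default. The proportion can therefore depend on a post-randomisation label and be biased if reasons differ by arm.

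The size depends on assumptions. Three to five lopsided dropouts, and in some configurations two, can move an uncorrected chi-square across 0.05 in either direction. With continuity correction most of the cases shown do not cross, although five against none does (0.141 to 0.032). One dropout per arm changes little.

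The documents do not support a claim that dropout labels will decide the trial's result. They give no dropout rate or split by arm, and the continuous HQ-CT comparison and its power do not use this rule. The change is worth making before unblinding because the gap lies in a stated rule and is cheap to close.

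**What to change.** In item 1b, replace the dropout sentence with one rule that does not depend on the reason: response is assessed at week 8; every randomised subject without a week-8 HQ-CT is a non-responder, whatever the reason; the denominator in each arm is all subjects randomised to it. Add one sensitivity analysis that multiply imputes the week-8 HQ-CT score and then applies the 30% threshold. State at the same time whether the chi-square is continuity-corrected.

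The cost is one or two sentences and one extra table. Response rates will be slightly lower. Assessments missed for reasons unrelated to treatment, including pandemic disruption, will count as failures in the main responder analysis. The rule removes the dependence on labels but not every bias from unequal loss, and the imputation analysis is there to show how far that matters.
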